## Planned Analyses

**Primary Outcome:** Number of patients vaccinated for influenza between enrollment date and target appointment date.

[ *Time Frame: Between the enrollment date and target appointment date (at least 4 days and up to 4 months)* ]

This field experiment will be conducted with Geisinger patients via SMS messages sent prior to their first flu shot-eligible appointment during the study period, referred to as the "target appointment." The key dependent variable is whether patients receive a flu shot at or before their target appointment (as recorded in their electronic health record).

If patients cancel or do not show up for their target appointment after they have been randomized to an arm and then schedule a new appointment during the study period, their new flu-shot eligible appointment becomes the target appointment and the outcome window extends from three days prior to the original appointment through the date of the new target appointment.

Patients who miss their target appointment and do not reschedule within the study period will still be included in the analysis. Their outcome window is from three days prior to the original appointment through the date of the original canceled appointment.

**Primary Question:** Are personalized flu shot messages more effective in increasing flu vaccination rates than the best-performing message in a prior megastudy (Reserved For You), an active control message, and/or no message?

**Secondary Question:** Among the Reserved For You message, the active control message, and no message, how do flu vaccination rates compare? Specifically, does the Reserved For You message lead to higher vaccination rates than both the active and passive control messages, and does the active control message result in higher rates than the passive control?

**Analysis (Confirmatory):** We will test the hypothesis that patients in different arms will exhibit different flu vaccination rates. Specifically, we will compare the following groups:

- Personalized Nudge
- Reserved For You Nudge
- Active Control
- Passive Control

For this analysis, one OLS regression model will be run in the following estimating equation:

$$Y_i = \beta_0 + \beta_1 ReservedForYou_i + \beta_2 ActiveControl_i + \beta_3 PassiveControl_i + \varepsilon_i$$

Where:

- $Y_i$ : Binary outcome variable for patient  $i$  (1 = vaccinated, 0 = unvaccinated)
- $\beta_0$ : Mean vaccination rate in the Personalized Nudge arm (reference category)

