**Heterogeneity Analyses (Exploratory):** We will conduct heterogeneity tests to determine if personalized nudges work better for certain subsets of the population. This will include, but not be limited to, examining factors such as:

- Alignment of the assigned personalized nudge with the received nudge: For participants in the Reserved For You or Active Control arms, we will evaluate whether the effectiveness of the intervention differs based on whether the nudge they received was predicted by the algorithm to be the most effective for them. For example:
  - Aligned: Participants randomized to the Reserved For You or Active Control arm, where the received nudge is the one predicted by the algorithm to be their optimal nudge
  - Misaligned: Participants randomized to the Reserved For You or Active Control arm, where the assigned nudge is not the one predicted by the algorithm to be their optimal nudge
- Feasibility Constraints: Receipt of the optimal nudge versus a different nudge due to feasibility constraints
- Pre-defined sub-groups: Patient groups based on demographic factors such as age and race
- Generalizability: We will assess how the effectiveness of the nudge varies across different clinical contexts, including:
  - Care Setting: The original flu shot megastudy was restricted to primary care target patient appointments. The current study also includes specialty care target appointments. We will compare the relative effectiveness of nudges among patients with target appointments in primary care vs. specialty care to determine whether the impact of nudges depends on the type of healthcare interaction.
  - Patient Population: We will compare the relative effectiveness of nudges among patients who were part of the original training set (i.e., patients in the megastudy) vs. those who are new to the current study to determine whether algorithm-driven predictions maintain validity in previously unseen patients.

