## Other Prespecified Outcomes

Similar exploratory analyses will also be run for the following outcomes, using the same OLS regression models described above.

1. Number of patients with flu shot receipt on or before December 31, 2024

[Time Frame: Up to 4 months after randomization]

2. Number of patients with flu shot receipt between enrollment date and first eligible appointment date

Patients received the flu shot at or before their first eligible appointment date (regardless of whether the patient rescheduled this appointment to a later date within the study period)

[Time Frame: 4 Days]

3. Number of patients with flu diagnosis (encounter diagnosis or flu test)

Patients received a flu diagnosis via encounter diagnosis or flu test between enrollment and April 30, 2025.

[Time Frame: Up to 8 months after randomization]

4. Number of patients with flu-related complications

Patients experienced flu-related complications before as defined by relevant diagnosis, hospitalization, or death, between enrollment and July 31, 2025 as recorded in the electronic health record

[Time Frame: Up to 11 months after randomization]

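### The exploratory care-setting subgroup is defined by the target appointment, which can be replaced after randomization; it should be defined by the first eligible appointment

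*SAP*

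**What the plan says.** The care-setting comparison is in the SAP under Planned Analyses, in the exploratory heterogeneity analyses (Generalizability, Care Setting): "We will compare the relative effectiveness of nudges among patients with target appointments in primary care vs. specialty care". It is there because the earlier megastudy covered primary care only, whereas "The current study also includes specialty care target appointments".

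The primary-outcome text of the same section defines the term in two steps. The messages precede the patient's "first flu shot-eligible appointment during the study period, referred to as the 'target appointment". Then comes the exception. It opens "If patients cancel or do not show up for their target appointment after they have been randomized to an arm", and for those who rebook within the study period "their new flu-shot eligible appointment becomes the target appointment". For them "the outcome window extends from three days prior to the original appointment through the date of the new target appointment". Patients who do not rebook keep the original date.

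Other Prespecified Outcomes, item 2, uses an anchor that does not move: "Patients received the flu shot at or before their first eligible appointment date", and this applies "regardless of whether the patient rescheduled this appointment to a later date within the study period".

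**The concern.** Randomization makes the arms comparable within subgroups that are fixed at baseline. Care setting is meant to be such a subgroup, but it is attached to a label that the plan itself can change after randomization. A patient enrolled on a primary care visit who cancels and rebooks in a specialty clinic would, on the literal wording, be analysed under specialty care.

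Two consequences need to be kept apart:

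- **Dilution.** If switching is equally common in every arm and involves the same kind of patient, each setting group is contaminated with patients from the other, and a real difference between settings is understated.
- **Bias.** If the arm influences cancelling or rebooking, the patients in a setting group are no longer comparable between arms, and the arm-by-setting contrast can be shifted in either direction.

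At stake is one exploratory question: whether the effect of the nudges depends on the type of visit.

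**Working it through.** The SAP states no figure for this comparison and no rate of cancelling, rebooking or changing setting, so there is nothing to reproduce. The first step is a reading of the text. The rest is arithmetic on assumptions, labelled as such.

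**1. The text.** The care-setting item uses the term target appointment without saying original or rebooked. The primary-outcome rule contrasts the original appointment with the new target appointment, and exploratory outcome 2 names the first eligible appointment separately. In this plan, then, the two are different things for a rebooker, and no sentence fixes care setting at randomization.

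**2. Dilution.** Assumptions: settings of equal size; true effects of 3 pp (primary care) and 1 pp (specialty), an interaction of 2.0 pp; a share m of each setting switches, equally in all arms, and switchers have the average effect of their original setting. Here m = share rebooking × share of rebookers who change setting.

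- Primary group: 3(1 − m) + 1·m
- Specialty group: 1(1 − m) + 3·m
- Estimated interaction: 2.0 × (1 − 2m)

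| Rebook × switch | m | Primary | Specialty | Interaction |
|---|---|---|---|---|
| 10% × 10% | 1% | 2.98 | 1.02 | 1.96 pp |
| 20% × 25% | 5% | 2.90 | 1.10 | 1.80 pp |
| 30% × 50% | 15% | 2.70 | 1.30 | 1.40 pp |

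**3. Bias when the arm affects rebooking.** Assumptions: equal settings, 25% vaccinated, no true message effect, no switching in the comparison arm, and in the messaged arm 1% of all patients move from specialty to primary care. The result depends on what is assumed about the movers. The interaction is primary minus specialty.

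- *A. Movers are vaccinated at 35% in either setting.* Primary: (0.50 × 0.25 + 0.01 × 0.35)/0.51 = 25.20%. Specialty: (0.50 × 0.25 − 0.01 × 0.35)/0.49 = 24.80%. Spurious interaction: +0.40 pp.
- *B. Rebooking lengthens the movers' window and lifts them from 25% to 35%.* Primary: 25.20% as before. Specialty: (0.50 × 0.25 − 0.01 × 0.25)/0.49 = 25.00%. Spurious interaction: +0.20 pp.

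A wider range, under A's assumption that a mover's rate v is the same in either setting: 27% vaccinated, and a share s of specialty patients moving to primary care. The primary rate is (0.27 + s·v)/(1 + s) and the specialty rate is (0.27 − s·v)/(1 − s). With s at 6% in one arm and 8% in the other:

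- v = 50%: primary 28.30% to 28.70%, specialty 25.53% to 25.00%; interaction +0.93 pp.
- v = 15%: primary 26.32% to 26.11%, specialty 27.77% to 28.04%; interaction −0.49 pp.

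The interaction is 0 if s is equal in both arms or if v is 27%.

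**4. With setting fixed by the first eligible appointment.** Misclassification from rebooking is 0 by construction, so the dilution in step 2 vanishes. Scenario A gives 0. Scenario B does not: primary is 25.0%, specialty is (0.49 × 0.25 + 0.01 × 0.35)/0.50 = 25.2%, and the interaction is −0.20 pp. That remainder comes from the outcome-window rule, not from the subgroup label.

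**5. Scale.** For two arms of 25,000 (SAP, Power analysis), an assumed 50:50 setting split and 27% vaccinated, the standard error of the interaction is √(4 × 0.27 × 0.73/12,500) = 0.79 pp. An interaction of (1.96 + 0.84) × 0.79 ≈ 2.2 pp would have 80% power.

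**The case against.** The strongest reply is that the plan may already mean the qualifying visit. It introduces the target appointment as the first eligible one, and the sentences just before the comparison use the term to describe which patients each study covered. That reading is possible, so the plan cannot be said to commit itself to the rebooked visit. But the care-setting item does not say so, and for rebookers the later rule displaces the first definition. If the sponsor does mean the first visit, the same sentence settles it.

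It can also be said that the SAP never describes a change of setting on rebooking, and that its talk of rescheduling fits the same visit being moved to another date. This stands as a limit on size: only rebookers who change setting are affected. Switching is not excluded, however, and both settings are in the study.

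Two stronger claims are tempting and are not supported:

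- A reader might infer that setting is measured after the messages. The text supports only after randomization: a cancellation may come before the text message, and passive control receives none.
- A reader might infer that switchers are counted in a setting their message did not concern. The SAP does not say whether rebookers are messaged again about the new visit.

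**Conclusion.** The point holds as a defect of definition in one exploratory subgroup. On its literal wording the plan classes some patients by a visit that became their target after randomization, although it has a fixed alternative at hand.

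The certain consequence, wherever patients change setting, is misclassification. With switching equal across arms this is dilution only: 2.0 to 1.8 pp at 5% each way, and to 1.4 pp only under heavy switching (30% rebooking, half of them changing setting), all with equal-sized settings assumed. Bias needs the further assumption that the arm alters rebooking. The size is unknown and may be small.

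A reader might take the 0.40 pp artefact as the expected bias. It is not: it requires movers who would be vaccinated at 35% in either setting. If the longer window is what raises their rate, the artefact is 0.20 pp. Either figure is about half or a quarter of the 0.79 pp standard error.

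Nor does the point reach the confirmatory pairwise comparisons, which do not use care setting. The longer outcome window for rebookers is a separate issue, and redefining the subgroup does not resolve it.

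**What to change.** In the Care Setting item, state that patients are grouped by whether their first eligible (original) appointment, as on file at randomization, was in primary or specialty care, whatever appointment later becomes the target. Leave the outcome-window rule for the primary outcome as it is.

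Run the same setting comparison on exploratory outcome 2 as well. Its window is tied to the first appointment, so a clear difference from the main result would point to the longer window for rebookers.

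The cost is one sentence of definition and one additional exploratory run. Outcome 2 already requires the first eligible appointment to be identified; its setting has to be kept with it. The SAP says that the extracted vaccination data have not yet been analysed, so the definition can be settled without knowledge of results if it is done before the preliminary analyses.

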### **Sensitivity analyses and robustness checks**

Statistical analyses will use an intent-to-treat approach, including all patients randomized. However, the analyses described above may also be run with the subset of patients who, according to text message records from Twilio, actually received all their messages as intended and attended their target appointment. This robustness check may exclude patients who were randomized but never sent messages for a variety of reasons (e.g., their phone numbers were inactive, they were on a do-not-contact list the research team did not have access to prior to randomization). This analysis may also exclude patients who received repetitions of the same message, received their texts late, or experienced other message distortions due to technical events outside the study team's control.

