### Methods

Patients eligible for the study as of September 9, 2024 were randomized to one of the following arms:

1. Personalized Nudge: nudge predicted to be most effective for the patient on the basis of the machine learning-derived treatment assignment
2. Reserved For You Nudge: nudge found to be on average most effective in the megastudy, including language that a flu vaccine is "reserved" for patients at their upcoming appointment
3. Active Control: a simple message notifying patients they can get a flu shot at their upcoming appointment
4. Passive Control: no message beyond the ambient healthcare system and public health campaigns to increase vaccination

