- $\beta_1$ : The difference in vaccination rate between the Reserved For You nudge arm and the Personalized Nudge arm
- $\beta_2$ : The difference in vaccination rate between the Active Control nudge arm and the Personalized Nudge arm
- $\beta_3$ : The difference in vaccination rate between the Passive Control nudge arm and the Personalized Nudge arm
- $\varepsilon_i$ : Error term for patient  $i$

Based on this model, we will assess the following pairwise comparisons:

- Personalized Nudge vs. Reserved For You Nudge
- Personalized Nudge vs. Active Control
- Personalized Nudge vs. Passive Control

To estimate the secondary comparisons between study arms (Reserved For You, Active Control, and Passive Control), post hoc pairwise tests will be conducted using the estimated marginal means from the primary OLS model:

- Reserved For You Nudge vs. Active Control
- Reserved For You Nudge vs. Passive Control
- Active Control vs. Passive Control

Recent work suggests that OLS regressions are appropriate in randomized experiments such as this one, using binary outcome variables (Gomila, 2021). We will estimate heteroskedasticity-robust standard errors.

We will not correct for multiple comparisons in the analyses above, as adjustment is not appropriate for individual testing. Each result must be statistically significant to reject its associated individual null hypothesis (Rubin, 2021). Thus, each significant result is an indicator of a specific null hypothesis rejection and has no direct bearing on the success of other hypotheses or the overall study.

EHR flu vaccination data have been finalized and extracted as of this writing but have not yet been analyzed. Insurance claims for flu vaccinations can take up to 90 days to process. To ensure completeness, we will extract the final flu vaccination claims data on April 1, 2025—90 days after the last appointments in the study—plus an additional day to account for potential data refresh delays. In the interim, we will extract an earlier dataset with flu vaccination claims data in the coming weeks for use in preliminary analyses. If there are discrepancies between EHR and claims data regarding vaccine dates, we will use EHR data unless the EHR record is marked as "historic." In such cases, we will use the claims data.

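### The optional message-receipt check has no rule for Passive Control, which is sent no messages, and it also conditions on attendance, which occurs after randomization

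*SAP*

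**What the plan says.** The SAP, under Sensitivity analyses and robustness checks, makes intent-to-treat on all randomized patients the main approach. It then permits a repeat of the same model and comparisons in a group picked out from the messaging log, namely those who "actually received all their messages as intended and attended their target appointment". It goes on: "This robustness check may exclude patients who were randomized but never sent messages for a variety of reasons". The reasons it gives include inactive phone numbers and that "they were on a do-not-contact list the research team did not have access to prior to randomization". Patients with late, repeated or distorted texts may also be removed.

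The Methods section defines the fourth arm as receiving "no message beyond the ambient healthcare system and public health campaigns to increase vaccination".

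The analyses being repeated are those under Planned Analyses: one four-arm OLS model and six pairwise comparisons. Three of the six have Passive Control on one side, among them "Personalized Nudge vs. Passive Control". For the main analysis, the same section states: "Patients who miss their target appointment and do not reschedule within the study period will still be included in the analysis".

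**The concern.** A criterion based on message receipt has no natural meaning in an arm that is sent nothing. The SAP neither gives that arm its own rule nor confines the check to the three message arms. An analyst must choose between dropping Passive Control and filtering only one side of the comparison. The second choice sets patients selected for being reachable against an unselected control group.

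The attendance condition is a separate problem. It can be applied in all four arms, but a text about the appointment may alter who attends. Attenders in different arms are then not comparable groups, and any of the six comparisons can be affected.

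At stake is how the trial is read, not its main result. If the check is run, it will be reported as a robustness result and taken as support for, or evidence against, the intent-to-treat finding. A difference created by selection could be mistaken for confirmation.

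**Working it through.** **Inputs from the SAP (Power analysis).** 15,000 patients in Passive Control and 25,000 in each other arm; 25% baseline rate; two-sided 0.05; 80% power; detectable effects of 1.3 points against Passive Control (25% to 26.3%) and 1.1 points between active arms (27.0% to 28.1%).

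**The SAP's own figures.** Solving a pooled-variance two-proportion test for 80% power gives 1.26 points for 15,000 versus 25,000 from 25%, and 1.12 points for 25,000 versus 25,000 from 27%. Both agree with the stated 1.3 and 1.1 after rounding. No figure in the SAP is disputed here; 1.3 points serves as the yardstick.

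**Reading A: the criterion applies to all arms.** Passive Control falls from 15,000 to 0. The Passive Control coefficient (β₃) and three of the six comparisons cannot be estimated.

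**Reading B: the message condition is waived for Passive Control.** The do-not-contact list was unavailable before randomization, so listed patients were randomized to all four arms. Patients with inactive phones are likewise in all four, but message records cannot identify them in an arm that was never texted. Unless a screen is applied separately to Passive Control, both groups leave the message arms and stay in Passive Control.

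Suppose there is no true effect, so every arm has a 25% rate. Let *u* be the share removed from a message arm and *r* the vaccination rate among those removed. Both are assumptions, since the SAP gives neither.

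- Rate among those kept: k = (0.25 − u·r)/(1 − u)
- Spurious difference: k − 0.25
- SE = √[0.25·0.75/15,000 + k(1 − k)/(25,000(1 − u))]
- Rejection rate: two-sided at 1.96

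| u | r | k | Spurious difference (points) | SE (points) | Called significant |
|---|---|---|---|---|---|
| any | 25% | 0.2500 | 0 | – | 5% |
| 3% | 20% | 0.2515 | +0.15 | 0.450 | 6.4% |
| 5% | 15% | 0.2553 | +0.53 | 0.453 | 21% |
| 10% | 10% | 0.2667 | +1.67 | 0.460 | 95% |

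Worked line for the middle case: (0.25 − 0.05·0.15)/0.95 = 0.2425/0.95 = 0.2553.

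**Attendance condition, applied in all arms.** Assume 85% attendance in Passive Control, a 5% vaccination rate in non-attenders, and texts that bring extra patients to the appointment without changing whether they are vaccinated.

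- Passive Control attenders: (0.25 − 0.15·0.05)/0.85 = 0.2425/0.85 = 0.2853
- Message arm, attendance +1 point: (0.2425 + 0.01·0.05)/0.86 = 0.2826; difference −0.27 points, significant 8.4% of the time
- Message arm, attendance +2 points: (0.2425 + 0.02·0.05)/0.87 = 0.2799; difference −0.54 points, significant 19% of the time
- If texts do not change attendance, the bias is zero.

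These examples treat the two conditions one at a time, and they push in opposite directions. The SAP applies both together, so the net sign cannot be predicted.

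**The case against.** The strongest reply is that Reading A is strained. Patients due no messages trivially received all of them as intended, and the exclusion for patients never sent messages is explained by delivery failures, not by design. That is a fair reading, but it leads straight to Reading B, where the filter acts on one side only.

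Second, the SAP does not say the do-not-contact list could not later be applied to all four arms. That is true, and such a screen would remove that part of the asymmetry. The SAP does not provide for it, and it would not cover inactive phones in patients who were never texted.

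Third, late or repeated texts caused by technical events may be unrelated to the tendency to vaccinate. In that case removing those patients causes no bias, and the problem comes mainly from inactive phones and do-not-contact status, which may be a small share.

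Fourth, every removal and attendance rate above is assumed, and the 95% figure needs both a large removal and a low rate among those removed. This stands: the table shows what is possible, not what is expected. The attendance example is also simplified, because attending is itself an opportunity to be vaccinated.

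Fifth, keeping non-attenders in the main analysis does not contradict dropping them in a robustness subset. Agreed. The objection to the attendance condition is that it comes after randomization, not that it is inconsistent with the main analysis.

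Finally, the check is optional and intent-to-treat is primary. Both are true and limit the severity, but neither repairs the subset rule if the check is run.

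**Conclusion.** The concern holds. As written, the check either cannot estimate the three Passive Control comparisons or, on the more natural reading, exposes them to selection bias; the attendance condition can bias all six. In the illustrations, the delivery filter produces a spurious +0.15 to +1.67 points (3–10% removed, vaccinating at 20% down to 10%) and the attendance filter −0.27 to −0.54 points, against a planned detectable effect of 1.3 points. These sizes rest wholly on assumed delivery and attendance rates. The bias vanishes if removed patients vaccinate like everyone else and texts leave attendance unchanged. The intent-to-treat analysis is not touched, so this is a change the SAP should make, not a threat to the primary result.

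**What to change.** Keep intent-to-treat on all randomized patients as the main analysis, and revise the check as follows.

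1. Limit the received-as-intended subset to the comparisons among the three message arms, and label it non-randomized.
2. Drop the attendance condition and report attendance by arm instead.
3. For each message arm against Passive Control, keep all randomized patients and report a complier-average estimate, with assignment as the instrument for delivery. Define delivery in advance, for example as at least one study message delivered. Late or repeated texts then count as delivered, which keeps the exclusion restriction plausible.
4. Apply a reachability or do-not-contact screen in comparisons with Passive Control only if it can be ascertained identically in all four arms.

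The cost is SAP wording and three two-stage models, using message records and outcome data the SAP already names. Precision falls slightly. With 25% versus 27% and an assumed 95% delivery, the intent-to-treat SE is √(0.25·0.75/15,000 + 0.27·0.73/25,000) = 0.451 points, a 95% half-width of 0.88. The complier estimate is 2.0/0.95 = 2.11 points with half-width 0.88/0.95 = 0.93, about 5% wider; z is about 4.43 for both. The complier estimate therefore gives an effect size among patients reached, not an independent test, and should be described that way.
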